11.1. Ethics Committee Approval

Ethics Committee (EC) approval or acknowledgement of the lead EC approval to participate in this trial is required from each institution joining this investigation. Prior to participant enrollment, a signed copy of the EC approval letter must be submitted to CLJI Worldwide certifying investigational plan approval. Investigators are responsible for submitting and obtaining initial and continuing review if necessary (at intervals not greater than once a year) of the clinical investigation by their reviewing EC.

11.2. Informed Consent

Subject Information/Informed Consent is mandatory and must be obtained from all subjects prior to their participation in this trial.

Any modifications to the Informed Consent must be approved by CLJI Worldwide, and as necessary by the EC. Copies of revised versions and the final Subject Information/Informed Consent must be provided to CLJI.

A copy of the EC approved Informed Consent along with a copy of each patient's signed consent must be maintained by each investigator. A signed copy of the consent form must be given to each participant.

11.3. Confidentiality

The participant's name and personal data will remain confidential and will not be published in any way. Participants will be identified on all e-CRFs by a unique reference number. E-CRFs are confidential documents. The sponsor's monitor or representative and regulatory and Ethics Committee representatives, auditors and inspectors may have access to medical files in order to verify authenticity of data collected. Accordingly, data will only be available to the sponsor, the Investigator, Investigators' staff, the investigation statistician, and if requested to the advisory committee and regulatory authorities.

The Investigator will maintain as part of the investigation file a list identifying all patients entered into the study.

11.4. Records and Reports

11.4.1. Records

Records to be maintained by the investigator include:

- Clinical trial investigational plan and all amendments, all approved versions
- Signed clinical trial agreement
- EC approval letter, including final informed consent
- EC membership list
- Correspondence relating to the trial

- CVs for all investigators and research coordinator
- Site personnel signature list
- Clinical monitor sign-in log
- Patient screening/enrollment log
- Reports (includes annual reports, final reports from investigator and sponsor)

The following records must be maintained for each participant enrolled in the trial:

- Signed Informed Consent (latest approved site version)
- All completed e-CRFs
- Supporting documentation of any complications and/or safety events.

CLJI Worldwide requests that the investigator retain copies of procedure reports, procedure nursing notes and the results of any interventional procedures that occurs post trial procedure. CLJI Worldwide reserves the right to secure data clarification and additional medical documentation on participants enrolled in this trial.

11.4.2. Reports

Adverse event reporting requirements are discussed in Section 7.4.

CLJI Worldwide will make reports on this investigation available to the DMC and Study Steering Committee when necessary and in accordance with the respective charters.

CLJI Worldwide must be notified within 24 hours of any unanticipated adverse device effects, withdrawal of EC approval or major protocol violations.

Upon completion or termination of the trial, the principal investigator for each site must submit a final written report to CLJI Worldwide and the Ethics Committee as required by the regulations. The report must be submitted within 3 months of completion or termination of the trial.

11.5. Protocol Deviations

The investigator will not deviate from the protocol without the prior written approval of CLJI Worldwide except in medical emergencies or in unforeseen, isolated instances where minor changes are made that will not increase the participant's risk or affect the validity of the trial. In medical emergencies, prior approval for protocol deviations will not be required, but the CLJI Worldwide clinical research personnel must be notified within 24 hours of the incident.

All protocol deviations need to be recorded in the respective section of the e-CRF and reported according national and ethics committee requirements. Periodic monitoring of protocol compliance will be performed for each site. The sponsor maintains the right to place a moratorium on enrollment in sites deemed to have excessive protocol compliance issues. In cases of major protocol violation, e.g., failure to obtain informed consent or violation of inclusion/exclusion criteria, the principal investigator is required to make a written statement attesting to retraining or other action(s) to be taken at his/her site to avoid such violations in the future.

11.6. Protocol Amendments

Changes to the protocol that may be made during the clinical study will be made by prior written agreement between CLJI Worldwide and the Principal Investigator. An amendment will be effective when: a) signed by the Principal Investigator and CLJI Worldwide and b) the amendment has been approved by the EC, if required by the Institution's policies.

Appendix 1: English master Informed Consent

Appendix 2: Daily Home PCR Instructions for Women

Thank you for volunteering for this study. Please read this sheet over carefully to understand how the study is being done.

Study Supplies

You will receive the following supplies:

- Dacron-tipped swabs (similar to Q-Tips®)
- Small plastic vials (with green, yellow, and red labels)
- Color coded labels
- A storage box
- VIBLOK cream
- Mirror
- A bag for transport
- A swab collection log
- A study diary

Sample Labels

The labels are preprinted with your study, clinic, and participant number. For each sample you collect, please fill in the date and time you collected the sample.

Study Diary

It is important that you bring your study diary to **each** clinic visit. Fill out the diary immediately before you obtain your swab samples. Please record this information as accurately as possible.

Storage of Samples

Vials with and without swabs can be stored at room temperature. When you return to the clinic for your next appointment, please bring the storage box with all the swab samples and your diary.

Communicating with the Clinic

If you develop symptoms of a recurrence or have any questions, please contact the **<specify the department>**. If you have ANY unusual urinary, genital, or rectal symptoms, such as a urinary tract infection, rash, or bleeding, call the clinic as soon as possible for an appointment. Every effort will be made to accommodate your schedule for clinic visits. Please call in at the earliest sign of symptoms so that a visit can be scheduled as soon as possible.

Weekdays: <specify contact information>

After Hours: <specify contact information>

Collecting Daily Swab Samples

Please read the following instructions carefully, it is very important that you collect samples in the same order as given in the instructions.

Please collect two extra-genital swabs per day: one **before** and one 5-60 minutes **after** VIBLOK application.

Please also collect a swab from a herpes **lesion** during an outbreak: do not apply VIBLOK when you develop a lesion and contact the clinic when you first notice symptoms.

Collect samples **once a day** before bathing or showering, or at least one hour after bathing or showering. Thoroughly wash and dry your hands before beginning.

[figure not shown]

Figure 2.1. Female genitals with VIBLOK application and swabbing area.

1/ To collect the **EXTRA GENITAL swab in the **green-labeled vial** **before** VIBLOK:**

1. Unwrap 1 sterile swab and hold it by the plastic shaft. Try not to touch the Dacron tip with your hands.

2. Gently put the swab on your labia.
3. Rotate the swab in a full circle. Gently remove the swab from your labia.
4. Rub the same swab from the outer (hairy) edges of your labia to the smooth skin below the vaginal opening, covering the entire area.
5. Rub the swab over the skin between your vagina and anal opening (anus).
6. Rub the swab in a circular motion over your rectal area, covering a radius of about 1.0 cm around the anus.

2/ Closing the vials and labeling:

1. Place the collected swab into the vial with the **green color coded** label.

2. Pull the swab out of the vial 0.5 cm, break (or cut) off the end of the plastic shaft, and discard it in the trash.
3. Securely replace the screw top of the vial.
4. Complete the swab collection log, with the full date (for example: 17-AUG-2015) and time of collection.
5. Place the labeled vial inside the grid box.

3/ Apply VIBLOK

1. Apply one packet of VIBLOK™ evenly and thoroughly to all external genital (including labia and clitoris), pubic, and perianal areas with or without hair.
2. Ensure application from minimally 2 cm outside of the outer (hairy) edges of your labia to the smooth skin below the vaginal opening, covering the entire area, the skin between your vagina and anal opening (anus), and your rectal area, covering a radius of about 2.5 cm around the anus. Apply more than one packet if needed.
3. Wait 5 to 60 minutes.

4/ To collect the **EXTRA GENITAL** swab in the **yellow-labeled** vial after VIBLOK:

1. Repeat the procedure as described under 1/ and 2/ using the vial with the **yellow color coded label**
2. Make sure to rub the swap only in the area where you applied VIBLOK: Keep a distance of at least 1 cm to the outer edges.
3. Use the mirror from your sampling kit if needed.

5/ To collect a **LESION** swab in the **red-labeled** vial:

If you develop a herpes lesion, please rub a separate swab over this area and place the swab in one of the **red-labeled** vials. Do **not** apply VIBLOK when you develop a herpes lesion and call the clinic when you first notice symptoms.

Repeat the procedure as described under 2/.

6/ After collection of the swabs

After you have collected the daily swabs, ensure to

1. thoroughly wash and dry your hands
2. have completed the participant diary

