5.2.4. Treatment - Follow-up call

Two-five days after visit 1, participants will receive a follow-up call by someone from the site research staff to verify that participants have a full understanding and no remaining questions concerning the study procedures, specifically with respect to:

- Swabbing procedures
- Application of the VIBLOK cream
- Completion of the diary

In addition, any AEs will be recorded.

5.2.5. Treatment – Visits 2 and 3

During the treatment periods, participants should:

- Complete their diary daily;

- Take swabs daily, before and 5-60 minutes after applying the cream on the external genitals according to the instructions;
- Visit the clinical trial site every other week

Clinical trial site visits will occur approximately 14 and 28 days after Visit 1.

During the clinic visits the following examinations/ evaluations and procedures will be done by site research staff:

- Adverse Events review;
- Targeted physical examination, including a genital examination that for women may include an internal genital examination if symptomatic;
- (Interim) medical history;
- Review and collection of subject's diary;
- Collection of subject swabs;
- Device accountability;

New trial devices and diary will be provided during Visit 2.

During Visit 3, subjects will be asked to complete a questionnaire regarding the usability of the cream (refer to Appendix 5).

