8.1.2. Risks/ Adverse Events associated with VIBLOK cream

In addition to the events listed in the previous section, the additional adverse events listed below are specifically associated with the VIBLOK cream and its application. The lack of data associated with long term VIBLOK usage prevents predicting the incidence of these risks. Additional complications include, but may not be limited to:

- Toxic, hypersensitive or allergic reaction

- Epithelial sensitization

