Appendix 4. Participant Diary

Day of the month	1	2	3	4	5	6	7	8	9	10
Time Skin Swab Collected										
Time VIBLOK Swab Collected										
Time in case of genital area shaved										
Time in case of genital area waxed										
Time in case of other hair removal										
Specify other hair removal method if applicable										
Anti-HSV medication taken										
Symptoms										
No Symptoms										
Itching, burning, tingling										
Lesions (sores, blisters, ulcers, crusts)										
Other (describe below)										
Lesion Locations										
Genital (Men: penis, scrotum; Women: vagina, labia, vulva, groin, pubis)										
Rectal (perineum, perianal)										
Buttock										
Other: _____										

Day of the month		11	12	13	14	15	16	17	18	19	20
Time Skin Swab Collected											
Time VIBLOK Swab Collected											
Time in case of genital area shaved											
Time in case of genital area waxed											
Time in case of other hair removal											
Specify other hair removal method if applicable											
Anti-HSV medication taken											
Symptoms											
No Symptoms											
Itching, burning, tingling											
Lesions (sores, blisters, ulcers, crusts)											
Other (describe below)											
Lesion Locations											
Genital (Men: penis, scrotum; Women: vagina, labia, vulva, groin, pubis)											
Rectal (perineum, perianal)											
Buttock											
Other: _____											

CLJI WORLDWIDE
 VIBLOK SAfety and perFormancE Trial Protocol
 Date 01/MAY/2017

Day of the month	21	22	23	24	25	26	27	28	29	30	31
Time Skin Swab Collected											
Time VIBLOK Swab Collected											
Time in case of genital area shaved											
Time in case of genital area waxed											
Time in case of other hair removal											
Specify other hair removal method if applicable											
Anti-HSV medication taken											
Symptoms											
No Symptoms											
Itching, burning, tingling											
Lesions (sores, blisters, ulcers, crusts)											
Other (describe below)											
Lesion Locations											
Genital (Men: penis, scrotum; Women: vagina, labia, vulva, groin, pubis)											
Rectal (perineum, perianal)											
Buttock											
Other: _____											

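### The daily diary has conflicting timing instructions and does not time symptoms relative to the cream, so short-lived local reactions have no designated place in it

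*Protocol*

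**What the plan says.** The home instruction sheets for women and men (Protocol Appendices 2 and 3, under Study Diary) carry the same line: "Fill out the diary immediately before you obtain your swab samples". The same sheets set the daily order: "Please collect two extra-genital swabs per day", one before the cream and one 5-60 minutes after it. Step 6, which follows the second swab, asks participants to make sure they "have completed the participant diary". Section 5.2.5 says only "Complete their diary daily".

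The diary (Appendix 4) has one column per day. It includes a row "Time VIBLOK Swab Collected" and a short symptom block: no symptoms, "Itching, burning, tingling", lesions, and a free-text row for anything else. It asks for no symptom start or stop time and states no recall period. It does not ask whether a symptom came before or after the cream.

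Section 8.1.2 lists as risks of the cream "Toxic, hypersensitive or allergic reaction" and epithelial sensitization. Section 8.1.1 lists local pain and itching as a complication of the infection itself. Type and duration of adverse events belong to the secondary safety endpoint (Protocol 3.2; the synopsis adds frequency, severity and causality). SAP 5.2.2 tabulates device-related events separately for during and after application, and SAP 5.2.3 lists the duration of each event.

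**The concern.** The diary is the only symptom record kept every day. If it does not show when a symptom arose relative to the cream, it cannot support a statement about local tolerability, and the timing has to come from somewhere else.

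This matters because non-serious local reactions are the main safety information the trial can realistically produce. The sample size section assumes an incidence of serious adverse device effects of 0.1%. With 46 treated participants that is 46 × 0.001 = 0.046 expected cases. SAP 5.2.2 itself expects very few or no serious adverse events. Section 8.1.2 says that the incidence of the listed cream reactions cannot be predicted for lack of data on long-term use.

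There is also a practical consequence. SAP 3.6 treats a diary not completed according to procedure as a protocol deviation, and sites cannot judge that consistently while the procedure contradicts itself.

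**Working it through.** The plan states no figure to reproduce. The check sets the instructions side by side and then does date arithmetic on the visit windows.

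**Step 1: daily order (Appendices 2 and 3).** Diary (by the Study Diary line), swab 1, cream, wait of 5-60 minutes, swab 2, then a check that the diary is complete (step 6). The row for the post-cream swab time cannot be filled before the cream. The Study Diary line therefore conflicts with step 6 and with the form.

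**Step 2: what a symptom tick means under each reading.**

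- *Entry before swab 1, describing that moment.* If entries are made at a similar time each day (an assumption), the previous cream was applied about one day earlier. A reaction that began after it and has cleared has no entry.
- *Entry before swab 1, covering the time since the last entry.* The reaction may be ticked, but in the next day's column, and nothing shows on which side of an application it fell.
- *Entry after swab 2.* A reaction within the 5-60 minute wait can be ticked, but in the same box as symptoms present before the cream. A later reaction passes to the next day.

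Under none of the three can an itching or burning tick be placed before or after the cream. Because the recall period is unstated, different participants may follow different readings.

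**Step 3: what is left when the diary does not capture the reaction.** The scheduled contacts at which adverse events are sought have these windows, in days after Visit 1 (Protocol 5.3): call 2-5, Visit 2 12-16, Visit 3 26-31. Shortest gap = earliest later contact minus latest earlier contact; longest gap = latest later contact minus earliest earlier contact.

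| Interval | Shortest | Longest |
|---|---|---|
| Visit 1 to call | 2 | 5 |
| Call to Visit 2 | 12 − 5 = 7 | 16 − 2 = 14 |
| Visit 2 to Visit 3 | 26 − 16 = 10 | 31 − 12 = 19 |

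Unless the participant phones the clinic, the type, frequency and duration of a brief reaction rest on recall over as much as 19 days.

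**Step 4: what the SAP needs.** Splitting device-related events into during and after application requires timing relative to the cream. The diary supplies none.

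**The case against.** The strongest reply is that the diary is not the adverse event instrument. Protocol 7.1 has events volunteered, elicited or observed. The follow-up call and both later visits ask for them, and the investigator judges causality (7.2). The home sheets also tell participants to phone promptly about any unusual genital symptom, giving rash as one example. This stands: reactions can reach the record by these routes. But the routes depend on a participant deciding to call (itching is not among the examples given) or on recall over the gaps above.

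A symptom entry before swab 1 also has a clear purpose. It fixes symptom status at the pre-cream swab, which the asymptomatic-day analyses can use. That stands too, and the fix keeps it.

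Some stronger readings are tempting, but the documents do not support them:

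- A reader might infer that the diary captures none of the reactions shorter than a day. That needs each entry to be a snapshot, and no section says so. The free-text row and step 6 also leave room for some entries.
- A reader might infer that the first day's entry precedes any exposure. Protocol 5.2.3 has the first application done at the site under observation, with the diary handed over afterwards.
- A reader might infer that the SAP counts cream reactions as herpes symptoms. SAP 4.3.2 tabulates diary symptoms as percentages of days without giving a cause, and SAP 5.2.2 analyses adverse events separately.
- A reader might infer that a cream reaction removes a day from the asymptomatic set. Neither document states how diary ticks define such a day, so this cannot be shown.

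**Conclusion.** The concern holds as a defect in data collection. The timing instructions contradict each other, and the only daily symptom record cannot place a local symptom before or after the cream. A reaction that begins after application and clears before the next entry has no designated place. It then depends on a call to the clinic or on recall at contacts 7-14 and 10-19 days apart.

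The effect falls on the secondary safety endpoint (type, frequency and duration of adverse events) and on the SAP's tables for events during and after application. The primary endpoint is unlikely to depend on the diary. The number of reactions that would be lost cannot be estimated, because the documents give neither their expected frequency nor their duration. The conclusion assumes roughly regular daily entry times and the visit windows as written. It is a cheap improvement worth making and does not threaten the trial's main conclusion.

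**What to change.** 1. Reconcile the Study Diary line in Appendices 2 and 3 with step 6 and with Appendix 4. The existing symptom rows should record status just before swab 1, and the swab-time rows should be completed afterwards.
2. Add one diary row, completed at the second swab and updated at the next day's entry: new itching, burning, redness or rash since applying the cream (yes/no, start time, stop time).
3. Have site staff review each positive entry at the next contact for adverse event recording, with the usual investigator causality assessment, and add a line to SAP 5.2 saying so.

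The new row gives timing. It does not by itself establish cause, because itching after application may still be due to herpes.

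The cost is one diary row, one corrected instruction in each sheet and one SAP line. Participants carry slightly more burden, and the reported rate of mild adverse events will probably rise. No extra visit or procedure is needed.

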Background	
Genital herpes has a high prevalence in industrialized as well as developing countries.
 
Genital herpes causes genital ulcers, increases risk for acquiring HIV infection, and may be transmitted mother to child during birth with possible serious consequences.
 
Medical treatments and condoms only partially reduce the risk for transmission from/ to sexual partners. Genital herpes transmission despite use of condoms is thought to be due to transfer via skin-to-skin contact in unprotected areas, and HSV-2 transmission may be enhanced by current shaving habits in the genital area leading to micro lesions (lacerations) of the skin.
 
VIBLOK™ is a cream designed to impede the passage of viruses, such as HSV-2, across the skin. Bench and animal experiments indicate that it can block virus transmission (HIV, HPV, HSV) up to 98%.
 
The objective of this clinical trial is to assess the safety and performance of VIBLOK in adults with HSV-2 infection by comparing virus detection in the extra-genital area before and after application of the barrier cream.

Primary objective	To assess safety of VIBLOK in HSV-2 infected adults.
Secondary objective	To evaluate the performance of VIBLOK as a barrier for virus transmission in men and women.
Study design	The VIBLOK SAfety and perFormancE Trial is a prospective, non-randomized, comparative multi-center safety and performance study. Up to 84 adults with a suspected HSV-2 infection are planned to be enrolled at up to 6 participating investigational centers in The Netherlands and Germany. Participants with a confirmed HSV-2 infection are planned to be followed for 26-31 days, using VIBLOK for minimally 26 days in a row. Safety will be assessed by collecting all adverse events, and HSV will be measured from daily self-collected external genital swabs before and after application of VIBLOK.
Study device	VIBLOK cream
Study scope	Minimally 1 and maximally 6 sites in The Netherlands and Germany are

	planned to participate in this study.
Study duration	The study is anticipated to last 12 months from first-subject-in to last-subject-out. Study participants are planned to be followed for 26 to 31 days.
Study Population	Adults with recurrent genital HSV-2 infections that meet all the inclusion and none of the exclusion criteria.
Number of subjects	Up to 84 men and women are to be enrolled, ensuring 46 participants with confirmed eligibility applying VIBLOK.

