2.1. Device Description

VIBLOK is a medical device, applied on the external genital, pubic, and perianal areas of men and women prior to sexual activity in order to cover minor cuts, scrapes and irritations of the skin including the ones associated with grooming of these areas, and to help protect against STIs caused by viruses such as Herpes Simplex. The main ingredients of the cream are a water repelling, high weight, silicone and a water repelling surface treated zinc oxide, similar to the zinc oxide used in diaper rash creams.

Figure 1 – VIBLOK cream package

The VIBLOK cream is supplied for single-use only, and is packaged in a sachet (Figure 1).

The VIBLOK cream is intended to be applied before sexual activity to all external genital, pubic, and perianal areas – with or without hair -, hereinafter referred to as “skin”, that will come in contact with the partner.

The CLJI VIBLOK cream shall be used per the Instructions for Use (IFU) and after training has been achieved as determined by the study sponsor. Further description of the VIBLOK cream is provided in the IFU and the Investigator’s Brochure (IB).

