5.1. Study Design

This is a prospective, non-randomized, comparative multi-center safety and performance trial. Up to 84 participants are planned to be enrolled at up to 6 participating investigational centers in Europe. The enrollment period is expected to be approximately 11 months and participant follow-up for subjects with a confirmed HSV-2 infection will last for 26 to 31 days. Participants will be assessed at the following intervals: at screening, during the first application, and approximately 14 and 28 days after first application.

Fourty six adults with recurrent genital herpes due to HSV-2 will be instructed to apply daily VIBLOK. Participants will obtain external genital skin swabs once daily, before and 5-60 minutes after applying the cream in the external genital area, and maintain a diary of genital signs and symptoms (Figure 3 and 4, Appendices 2, 3, and 4).

[figure not shown]

Figure 3: Female genitals with the VIBLOK application area (grey)

[figure not shown]

Figure 4: Male genitals with the VIBLOK application area (grey)

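### From day 2 the plan does not ensure that the 'before' swab is free of the previous day's cream, so the performance comparison may be pulled towards no effect

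*Protocol*

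**What the plan says.** Participants "will be instructed to apply daily VIBLOK" (Protocol 5.1), and the synopsis has them "using VIBLOK for minimally 26 days in a row". Protocol 5.2.5 tells them: "Take swabs daily, before and 5-60 minutes after applying the cream on the external genitals according to the instructions". Below, swab 1 is the daily swab before application (green label) and swab 2 the one after it (yellow label).

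Appendix 2 (women) and Appendix 3 (men) give the same timing rule for sampling: "before bathing or showering, or at least one hour after bathing or showering". The only washing they ask for is of the hands: "Thoroughly wash and dry your hands before beginning", and after the swabs "thoroughly wash and dry your hands". Protocol 2.1 describes the main ingredients as "a water repelling, high weight, silicone and a water repelling surface treated zinc oxide".

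The diary (Appendix 4) has rows for swab times, shaving, waxing, other hair removal, medication, symptoms and lesion sites, but none for washing. For each person, the detection endpoint is the number of swabs positive only before application minus the number positive only after, compared with zero by the Wilcoxon signed-rank test (Protocol 9.1; SAP 1.3 and 4.2). The SAP's rule on implausible swab data (2.3) does not mention residual cream, and SAP 4.2 and 4.3 contain no analysis by washing or by time since the previous application. SAP 4.3 does look at time since application, but only for swab 2.

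**The concern.** The comparison reads swab 1 as skin without cream. That is certain on Day 1, when swab 1 precedes the first application at the site. On later days it depends on whether the participant has washed since the last application and whether the wash took the film off. The plan secures neither.

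If some barrier remains, swab 1 is itself partly blocked. Positives are lost from the pre-only count, the within-person difference shrinks, and the product looks weaker than it is. The size would vary between people with their hygiene habits, and no visible record would let the analyst find the affected days. The two performance endpoints are secondary, but they are the trial's only performance evidence and are meant to support the CE mark (Protocol 1.1 and 3). If the test missed significance, a weak product could not be told from a partly blocked comparator.

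**Working it through.** **Inputs from the plan** (Protocol 9.1; SAP 1.4 and 2.8): 8% shedding rate, 50% reduction (so 4% after application), 40 participants, 28 days, 80% power, two-sided 5% test.

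**The plan's own figure.** The 40 participants can be neither confirmed nor refuted. The documents give no between-person spread, no pre/post discordance and no standard error. Simulating the signed-rank test without carry-over, over a range of assumptions for these, gave power between about 58% and 100% at n = 40. About 80% is reached, for example, with swabs 1 and 2 independent given the person's own rate and rates following a beta distribution with mean 8% and precision 1.

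**Apparent reduction.** Let f be the assumed fraction of the fresh 50% blocking that survives to the next swab 1.

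- Share of swab-1 detections lost: r = 0.5 × f
- Swab-1 rate: 8% × (1 − r); the swab-2 rate stays at 4%
- Apparent reduction: 1 − 0.5 / (1 − r)
- Mean net difference per person: 28 × (swab-1 rate − 4%)

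| f | r | Swab-1 rate | Apparent reduction | Net difference per person | Power, one scenario |
|---|---|---|---|---|---|
| 0% | 0% | 8.0% | 50% | 1.12 | about 83% |
| 20% | 10% | 7.2% | 44% | 0.90 | about 73% |
| 40% | 20% | 6.4% | 37.5% | 0.67 | about 59% |
| 60% | 30% | 5.6% | 29% | 0.45 | about 39% |

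The power column uses the independent-swab, precision-1 scenario. Repeat runs gave 80 to 84, 73 to 74, 59 to 61 and 36 to 39%.

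**Dependence on the scenario.** At f = 50% (r = 25%, apparent reduction 33%), three scenarios that start at 80 to 86% power end at different places:

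- independent swabs, precision 1: 80% falls to 49%
- swabs independent given shedding that day, precision 0.5: 84% falls to 59%
- swab-2 positives nested within swab-1 positives, precision 0.5: 86% falls to 74%

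**Partial exposure.** If only a share w of pairs is exposed, the average loss is r = w × 0.5 × f. With half the pairs exposed and f = 40%, r = 0.5 × 0.5 × 0.4 = 10%, and the apparent reduction is 44%.

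**Day 1 alone cannot replace the series.** It yields about 40 × 0.08 = 3.2 expected positive swab 1s.

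**The case against.** - **The bathing rule already covers many people.** For someone who bathes daily, either permitted order puts a bath between one application and the next swab 1. This stands. The exposed participants are those who skip a day or whose wash does not remove the film. A reader might infer that every pair after Day 1 is compromised; the documents do not support that.
- **Persistence may be near zero.** The plan says nothing about how long the barrier lasts beyond the 5 to 60 minute sampling window. This stands, and f = 0 belongs in the range.
- **Removal may be covered elsewhere.** The Instructions for Use, instruction video, training materials, swab collection log and Data Handling and Presentation Plan are cited but not among the documents. This stands as a limit. Even so, Appendices 2 and 3 are the step-by-step home procedure, and the step is absent there.
- **The bias is conservative and may be offset.** Residual cream cannot create a false benefit. Swab 1 rubs the same skin and may remove virus before swab 2, which acts the other way. So a reader should not infer that the trial will understate the effect overall. An opposite, unmeasured bias does not repair the comparator.
- **A steeper power loss is tempting.** Back-solving a standard error from the 80% power and holding it fixed would give about 61, 39 and 20% for r = 10, 20 and 30%. The plan states no standard error, and fewer swab-1 positives also reduce the variance, so those figures are too pessimistic.
- **Day 1 is not necessarily the only clean day.** Participants are told not to apply VIBLOK when a lesion develops and may re-enter after treatment (Protocol 5.2.6), so a re-entry swab 1 can also follow a cream-free interval.

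**Conclusion.** The gap is real. As written, a participant can follow every visible instruction and take swab 1 over the previous day's cream, and the visible data forms would not show it. Taken by itself, this biases the detection comparison towards no effect. The net bias of the before/after comparison is not established.

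The size is unknown. A true 50% reduction would appear as 44, 37.5 or 29% if 20, 40 or 60% of the fresh blocking persisted in all pairs, and as 50% if none did. The power loss rests further on an assumed between-person spread and pre/post dependence, and is smaller in some scenarios. Because the endpoints are secondary and study success rests on SADE incidence alone (SAP 5.2.1), this should be corrected but does not threaten the primary analysis.

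**What to change.** 1. **Appendices 2 and 3.** State that the swab area is to be washed after the last application and at least one hour before the next day's swab 1. The one-hour gap is the plan's own interval. Do not ask for washing straight after swab 2, because that could shorten the skin exposure behind the primary safety endpoint. Align the wording with the Instructions for Use and training material on how the cream comes off.
2. **Diary (Appendix 4).** Add one row: time area last washed.
3. **SAP 4.2.2.** Add a sensitivity analysis of the detection-rate and copy-number comparisons, limited to pairs with a recorded wash since the previous application.

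The cost is one instruction, one diary row, one extra analysis, slightly more participant burden and a protocol amendment. The restricted analysis will have fewer pairs, and a recorded wash does not prove that all cream is gone, so it reduces the problem without removing it.
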